#### **10.1.5 Dissemination of Clinical Study Data**

- A CSR will be developed by the Sponsor at completion of data analysis. This report will be a clinical and statistical integrated report, according to the ICH E3 guidelines.
- Sponsor will register the study and post study results regardless of outcome on a publicly accessible website (e.g., [clinicaltrials.gov](https://clinicaltrials.gov)) in accordance with the applicable laws and regulations.

#### **10.1.6 Data Quality Assurance**

- All subject data relating to the study will be recorded on printed or electronic eCRF unless transmitted to the Sponsor or designee electronically (e.g., laboratory data). The Investigator is responsible for verifying that data entries are accurate and correct by physically or electronically signing the eCRF.
- The Investigator must maintain accurate documentation (source data) that supports the information entered in the eCRF.
- The Investigator must permit study-related monitoring, audits, HREC review, and regulatory agency inspections and provide direct access to source data documents.
- Monitoring details describing strategy (e.g., risk-based initiatives in operations and quality such as Risk Management and Mitigation Strategies and Analytical Risk-Based Monitoring), methods, responsibilities, and requirements, including handling of noncompliance issues and monitoring techniques (central, remote, or on-site monitoring) are provided in the Monitoring Plan.

- The Sponsor or designee is responsible for the data management of this study including quality checking of the data.
- The Sponsor assumes accountability for actions delegated to other individuals (e.g., Contract Research Organizations).
- Study monitors will perform ongoing source data verification to confirm that data entered into the eCRF by authorized site personnel are accurate, complete, and verifiable from source documents; that the safety and rights of subjects are being protected; and that the study is being conducted in accordance with the currently approved protocol and any other study agreements, ICH GCP, and all applicable regulatory requirements.
- Records and documents, including signed ICFs, pertaining to the conduct of this study must be retained by the Investigator per ICH-GCP and local regulations or institutional policies. No records may be destroyed during the retention period without the written approval of the Sponsor. No records may be transferred to another location or party without written notification to the Sponsor.

#### **10.1.7      Source Documents**

- Source documents provide evidence for the existence of the subject and substantiate the integrity of the data collected. Source documents are filed at the Investigator's site.
- Data reported on the eCRF or entered in the eCRF that are transcribed from source documents must be consistent with the source documents or the discrepancies must be explained. The Investigator may need to request previous medical records or transfer records, depending on the study. Also, current medical records must be available.
- Source documents are original documents, data, and records from which the subject's eCRF data are obtained. These include but are not limited to hospital records, clinical and office charts, laboratory and pharmacy records, diaries, microfiches, radiographs, and correspondence.

#### **10.1.8      Study and Site Start and Closure**

The study start date is the date on which the clinical study will be open for recruitment of subjects.

The first act of recruitment is the first site open and will be the study start date.

The Sponsor designee reserves the right to close the study site or terminate the study at any time for any reason at the sole discretion of the Sponsor, else study sites will be closed upon study completion. A study site is considered closed when all required documents and study supplies have been collected and a study-site closure visit has been performed.

The Investigator may initiate study-site closure at any time, provided there is reasonable cause and sufficient notice is given in advance of the intended termination.

Reasons for the early closure of a study site by the Sponsor or Investigator may include but are not limited to:

- Failure of the Investigator to comply with the protocol, the requirements of the HREC or local health authorities, the Sponsor's procedures, or GCP guidelines
- Inadequate recruitment of subjects by the Investigator
- Discontinuation of further study intervention development

If the study is prematurely terminated or suspended, the Sponsor shall promptly inform the Investigators, the HREC(s), the regulatory authorities, and any contract research organization(s) used in the study of the reason for termination or suspension, as specified by the applicable regulatory requirements. The Investigator shall promptly inform the subject(s) and should assure appropriate subject therapy and/or follow-up.

#### **10.1.9      Publication Policy**

The publication policy for this study is located within the Clinical Study Agreement with the Investigator and/or Institution.

## 10.2 APPENDIX 2: CLINICAL LABORATORY TESTS

- The clinical laboratory tests detailed in [Table 5](#) will be performed by a central laboratory at timing/frequency detailed in the SoA (Section [1.3](#))
- Additional tests may be performed at any time during the study as determined necessary by the Investigator or required by local regulations.
- Investigators must document their review of each laboratory safety report

**Table 5: Clinical Safety Laboratory Tests**

Hematology	
White blood cell count (WBC) with differential (neutrophils, lymphocytes, monocytes, eosinophils, basophils – absolute and %)	Red blood cell (RBC) RBC Indices: MCV, MCH, %Reticulocytes
Haemoglobin	Haematocrit
Platelet count	
Clinical Chemistriesa	
Electrolytes: Sodium, Potassium, CO 2 or bicarbonate, Chloride, Calcium, Magnesium, Phosphorus,	
Liver function: Alkaline Phosphatase, alanine aminotransferase (ALT), aspartate aminotransferase (AST), Total Bilirubin	
Renal function: Blood Urea Nitrogen, Creatinine, Creatine Kinase, calculated Creatinine Clearance Cockcroft-Gault	
Other: Albumin, lactate dehydrogenase (LDH), non-fasting Glucose, uric acid, lactate dehydrogenase, total protein, total cholesterol, and triglycerides	
Urinalysis	
Basic Urinalysis (dipstick, including macroscopic appearance, bilirubin, blood, colour, glucose, ketones, leukocyte esterase, nitrite, pH, protein, specific gravity, urobilinogen;	Full urinalysis (dipstick plus microscopic evaluation) to be performed only at the Screening and End of Study visits). A reflex microscopic urinalysis should be performed if the result of the urinalysis is abnormal or at the discretion of the PI or delegate.
Other Study-Specific Laboratory Assessments	
Serum and urine human chorionic gonadotropin (hCG) pregnancy test	Serology
Syphilis screening test (rapid plasma regain)	HIV antibody, hepatitis B surface antigen (HBsAg), hepatitis C virus antibody or HCV RNA (qualitative)

## 10.3 APPENDIX 3: AES AND SAEs: DEFINITIONS AND PROCEDURES FOR RECORDING, EVALUATING, FOLLOW-UP, AND REPORTING

### 10.3.1 Definition of AE

#### AE Definition

- An AE is any untoward medical occurrence in a subject or clinical study subject, temporally associated with the use of study intervention, whether or not considered related to the study intervention.
- NOTE: An AE can therefore be any unfavourable and unintended sign (including an abnormal laboratory finding), symptom, or disease (new or exacerbated) temporally associated with the use of study intervention.

#### Events Meeting the AE Definition

- Any abnormal laboratory test results (hematology, clinical chemistry, or urinalysis) or other safety assessments (e.g., ECG, radiological scans, vital signs measurements), including those that worsen from baseline, considered clinically significant in the medical and scientific judgment of the Investigator (i.e., not related to progression of underlying disease).
- Exacerbation of a chronic or intermittent pre-existing condition including either an increase in frequency and/or intensity of the condition.
- New conditions detected or diagnosed after study intervention administration even though it may have been present before the start of the study.
- Signs, symptoms, or the clinical sequelae of a suspected drug-drug interaction.
- Signs, symptoms, or the clinical sequelae of a suspected overdose of either study intervention or a concomitant medication. Overdose per se will not be reported as an AE/SAE unless it is an intentional overdose taken with possible suicidal/self-harming intent. Such overdoses should be reported regardless of sequelae.
- “Lack of efficacy” or “failure of expected pharmacological action” per se will not be reported as an AE or SAE. Such instances will be captured in the efficacy assessments. However, the signs, symptoms, and/or clinical sequelae resulting from lack of efficacy will be reported as AE or SAE if they fulfil the definition of an AE or SAE.

### Events NOT Meeting the AE Definition

- Any clinically significant abnormal laboratory findings or other abnormal safety assessments which are associated with the underlying disease, unless judged by the Investigator to be more severe than expected for the subject's condition.
- The disease/disorder being studied or expected progression, signs, or symptoms of the disease/disorder being studied, unless more severe than expected for the subject's condition.
- Medical or surgical procedure (e.g., endoscopy, appendectomy): the condition that leads to the procedure is the AE.
- Situations in which an untoward medical occurrence did not occur (social and/or convenience admission to a hospital).
- Anticipated day-to-day fluctuations of pre-existing disease(s) or condition(s) present or detected at the start of the study that do not worsen.

### 10.3.2 Definition of SAE

If an event is not an AE per definition above, then it cannot be an SAE even if serious conditions are met (e.g., hospitalization for signs/symptoms of the disease under study, death due to progression of disease).

#### A SAE is defined as any untoward medical occurrence that, at any dose:

##### a. Results in death

##### b. Is life-threatening

The term 'life-threatening' in the definition of 'serious' refers to an event in which the subject was at risk of death at the time of the event. It does not refer to an event, which hypothetically might have caused death, if it were more severe.

##### c. Requires inpatient hospitalization or prolongation of existing hospitalization

- In general, hospitalization signifies that the subject has been detained (usually involving at least an overnight stay) at the hospital or emergency ward for observation and/or treatment that would not have been appropriate in the physician's office or outpatient setting. Complications that occur during hospitalization are AEs. If a complication prolongs hospitalization or fulfills any other serious criteria, the event is serious. When in doubt as to whether "hospitalization" occurred or was necessary, the AE should be considered serious.
- Hospitalization for elective treatment of a pre-existing condition that did not worsen from baseline is not considered an AE.

##### d. Results in persistent disability/incapacity

- The term disability means a substantial disruption of a person's ability to conduct normal life functions.

- This definition is not intended to include experiences of relatively minor medical significance such as uncomplicated headache, nausea, vomiting, diarrhea, influenza, and accidental trauma (e.g., sprained ankle) which may interfere with or prevent everyday life functions but do not constitute a substantial disruption.

**e. Is a congenital anomaly/birth defect**

**f. Other situations (Medically important):**

- Medical or scientific judgment should be exercised in deciding whether SAE reporting is appropriate in other situations such as important medical events that may not be immediately life-threatening or result in death or hospitalization but may jeopardize the subject or may require medical or surgical intervention to prevent one of the other outcomes listed in the above definition. These events should usually be considered serious.
- Examples of such events include invasive or malignant cancers, intensive treatment in an emergency room or at home for allergic bronchospasm, blood dyscrasias or convulsions that do not result in hospitalization, or development of drug dependency or drug abuse.

### **10.3.3 Recording and Follow-Up of AE and/or SAE**

#### **AE and SAE Recording**

- When an AE/SAE occurs, it is the responsibility of the Investigator to review all documentation (e.g., hospital progress notes, laboratory reports, and diagnostics reports) related to the event.
- The Investigator will then record all relevant AE/SAE information in the eCRF within 24 hours of Investigator/site awareness of the event.
- It is **not** acceptable for the Investigator to send photocopies of the subject's medical records to the Sponsor in lieu of completion of the AE/SAE eCRF page.
- There may be instances when copies of medical records for certain cases are requested by the Sponsor. In this case, all subject identifiers, except for the subject number, will be redacted on the copies of the medical records before submission to the Sponsor.
- The Investigator will attempt to establish a diagnosis of the event based on signs, symptoms, and/or other clinical information. Whenever possible, the diagnosis (not the individual signs/symptoms) will be documented as the AE/SAE.

### Assessment of Intensity

AE severity will be evaluated by the Investigator in accordance with the NCI CTCAE v5.0^1. For AEs that are not adequately addressed in the NCI CTCAE, the Investigator should classify the intensity of the AE using the following guidelines:

- Grade 1: Mild: Aware of sign or symptom, but easily tolerated; no intervention needed
- Grade 2: Moderate: Discomfort enough to cause interference with usual activity, minimal non-invasive intervention indicated (e.g., short course of antibiotics)
- Grade 3: Severe: Medically significant but not immediately life-threatening; incapacitation with inability to work or do usual activity
- Grade 4: Life-threatening: Refers to an event in which the subject was at risk of death at the time of the event, as judged by the Investigator; urgent/emergent intervention indicated. This category should not be used for an event that hypothetically might have caused death if it were more severe.
- Grade 5: Fatal outcome.

It will be left to the Investigator's clinical judgment to determine whether an AE is of sufficient severity to require the subject's removal from treatment or from the study. A subject may also voluntarily withdraw consent from treatment due to what she/he perceives as an intolerable AE. If either of these situations arises, the subject should be strongly encouraged to undergo an end-of-study assessment and be under medical supervision until symptoms cease or the condition becomes stable. An event is defined as 'serious' when it meets at least 1 of the predefined outcomes as described in the definition of an SAE, NOT when it is rated as severe.

### Assessment of Causality

- The Investigator is obligated to assess the relationship between study intervention and each occurrence of each AE/SAE.
- A "reasonable possibility" of a relationship conveys that there are facts, evidence, and/or arguments to suggest a causal relationship, rather than a relationship cannot be ruled out.
- The Investigator will use clinical judgment to determine the relationship.
- Alternative causes, such as underlying disease(s), concomitant therapy, and other risk factors, as well as the temporal relationship of the event to study intervention administration will be considered and investigated.
- The Investigator will also consult the Investigator's Brochure (IB) and/or Product Information, for marketed products, in his/her assessment.

 Please refer to the CTCAE v5 published on November 2017 at:  
[https://ctep.cancer.gov/protocolDevelopment/electronic\\_applications/docs/CTCAE\\_v5\\_Quick\\_Reference\\_5x7.pdf](https://ctep.cancer.gov/protocolDevelopment/electronic_applications/docs/CTCAE_v5_Quick_Reference_5x7.pdf) .

- For each AE/SAE, the Investigator **must** document in the medical notes that he/she has reviewed the AE/SAE and has provided an assessment of causality.
- There may be situations in which an SAE has occurred, and the Investigator has minimal information to include in the initial report to the Sponsor. However, it is important that the Investigator always make an assessment of causality for every event before the initial transmission of the SAE data to the Sponsor.
- The Investigator may change his/her opinion of causality considering follow-up information and send an SAE follow-up report with the updated causality assessment.
- The causality assessment is one of the criteria used when determining regulatory reporting requirements.

#### Causality Categories:

- **Related:** An event is considered related if there is a reasonable possibility of causal association between the study intervention and the event. This means there is evidence to suggest a causal relationship between the study intervention and the AE. The AE follows a reasonable temporal sequence from the time of study intervention administration and follows a known response to the study intervention and cannot be reasonably explained by other factors such as the subject's clinical state or other therapeutic interventions, or concomitant drugs administered to the subject.
- **Not related:** The available evidence support that the event is related to other factors such as the subject's clinical state, therapeutic interventions or concomitant drugs administered to the subject.

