### 2.3.1 Risk Assessment

There are no identified or potential risks of particular severity anticipated based on toxicological data with SUPLEXA in animals, nor based on the mechanism of action and composition (an autologous population of NK and  $\gamma\delta$  T cells, CD8-positive and CD4-positive cells). Additionally, these cellular components have individually been evaluated in clinical studies and found to be well tolerated based on the lack of SAE (Section 2.2).

SUPLEXA is a first-in-class non-engineered autologous cell therapy. This study is ongoing and as of Sept 19 2022, more than 15 subjects were enroled in the study and received from 3 to 6 doses of SUPLEXA. No treatment-related SAE or adverse events had been reported.

Although nothing has been observed to date in blood chemistry, urinalysis, hematological or any labs, nor in any reported AE/SAE, potential risks based on the ongoing study and theoretical concerns that may be associated are presented below (Table 1) based on studies involving the autologous administration of CTL (Ohtani, 2014), CAR-T (Shivani, 2018) and dendritic cells

(Anguille, 2014) as well as the allogeneic administration of NK cells (Kyle B. Lupo, 2019), and  $\gamma\delta$  T cells (Pauza, 2018).

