#### **4.3 DOSE JUSTIFICATION FOR SUPLEXA THERAPEUTIC CELL DOSE**

The initial cumulative dose selected for this study was based entirely on preclinical mouse xenograft studies in which we dosed mice at ~28x the intended human regimen 3 clinical doses with an option to extend to 6 doses, with each dose approximately 2.5 B cells (range 1.9-3.9 B cells). Given the complete absence of treatment related adverse events for SUPLEXA in the ongoing human study, we propose that after the first 3 doses, administration of up to 14 additional treatments of 5B cells every 2 weeks will be well tolerated, and the actual number of doses depends on the SUPLEXA manufacturing yields for each of 2 patient-specific SUPLEXA batches.

The DSMB will provide an additional review of all safety data and predetermined points in the progress of the clinical study.

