## 6.5 DOSE LIMITING TOXICITY CRITERIA

A DLT is defined as the occurrence or start of any of the events listed below during the treatment of the first 3 subjects in each cohort that are assessed as related to study intervention (SUPLEXA) by the Investigator or the Sponsor. An AE should not be considered as a DLT if it can reasonably be attributed to underlying disease, disease progression, concomitant medications, or other extraneous causes. Worsening of pre-existing medical illness could be due to study intervention and should not be excluded from consideration as a DLT.

The first 15 subjects will be assessed for DLT. For each subject, the DLT assessment period will comprise of 2 parts as follows (Refer to [Figure 5](#)):

- The first DLT assessment period – 1 week after the first dose (prior to administration of the second dose).
- The second DLT assessment period - 1 week after the second dose (prior to the administration of the 3rd dose)

Subjects who withdraw before the end of the DLT assessment period for reasons other than DLTs will be replaced.

All toxicities will be graded by the local site Investigator using National Cancer Institute (NCI) common terminology criteria for adverse events (CTCAE) v5.0.

The following will be considered DLTs:

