## 7 STOPPING RULES, DISCONTINUATION OF STUDY INTERVENTION AND SUBJECT WITHDRAWAL FROM THE STUDY

### 7.1 STUDY STOPPING RULES

Enrolment in this study will be stopped at any time for safety reasons.

The study includes DLT Stopping rules (refer to Section [6.5.1](#)). In addition, enrolment and treatment with SUPLEXA will be temporarily suspended for any of the following reasons pending review and recommendations from the DSMB:

- Any death that is not due to disease progression within 30 days after receiving SUPLEXA will result in a hold of further enrolment, until an investigation into the cause of death is performed by DSMB. If it is determined that the death was not related to the study intervention, then enrolment may restart. If the relationship between SUPLEXA infusion and death is not clear, or it appears that the death may be related to study intervention, enrolment will be held until further review. Refer to Section [8.3.7](#).
- The occurrence of two  $\geq$  Grade 4 DLTs in 2 study subjects.
- At least 3 cases of  $\geq$ Grade 3 of the following events assessed as related to study intervention:
  - Immunological related events
  - CRS
  - TLS

Suspension of the study will entail stopping the enrolment of new subjects and maintaining enroled subjects in the study. Suspension of the study will not entail cessation of dosing in subjects who did not complete the 3-dose administration unless so directed by the regulatory agencies or advised by the DSMB and agreed to by the Sponsor. The suspension will remain in effect until the case(s) and supporting information have been discussed between the Sponsor and the DSMB and the relevant regulatory agencies, if applicable, with a decision made to either resume the study or stop the study. If a decision is made to stop the study, all subjects will immediately discontinue dosing with study intervention and will undergo a follow-up visit as specified in the SoA.

The DSMB will review safety data at regular intervals, and can recommend, in its judgment, halting the study for any substantial imbalance in AEs. Sponsor additionally reserves the right to stop the study at any time for any reason. The regulatory health authorities and Australian Human Research Ethics Committee (HREC) will be notified in the event the study is stopped.

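### The causality categories in Section 10.3.3 contradict each other and leave an unexplained new event in neither category, so read literally they under-count related events in a first-in-human trial, most of all unexpected ones.

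*Combined protocol and SAP*

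**What the plan says.** The protocol sets the causality standard twice in Section 10.3.3.

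- **Assessment of Causality.** A reasonable possibility "conveys that there are facts, evidence, and/or arguments to suggest a causal relationship"; that a relationship cannot be ruled out is not enough. Alternative causes and timing are to be considered and investigated, the Investigator's Brochure (IB) is to be consulted, and clinical judgment decides.
- **Causality Categories, *Related*.** "An event is considered related if there is a reasonable possibility of causal association between the study intervention and the event". The definition then says that the AE has a reasonable temporal sequence and "follows a known response to the study intervention and cannot be reasonably explained by other factors such as the subject's clinical state", other therapeutic interventions or concomitant drugs.
- **Causality Categories, *Not related*.** "The available evidence support that the event is related to other factors such as the subject's clinical state", therapeutic interventions or concomitant drugs.

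There is no third category and no default.

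The classification is used elsewhere. A DLT must be "assessed as related to study intervention (SUPLEXA) by the Investigator or the Sponsor" (Section 6.5). One hold rule counts Grade 3 or higher cases "of the following events assessed as related to study intervention" (Section 7.1). On experience so far, Section 2.3.1 reports for more than 15 subjects: "No treatment-related SAE or adverse events had been reported". Section 4.3 begins its case for the later 5-billion-cell infusions with "Given the complete absence of treatment related adverse events for SUPLEXA in the ongoing human study".

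**The concern.** In a first-in-human study, safety monitoring exists chiefly to detect reactions that nobody has yet described. A requirement that an event match a known response works against that purpose, because the first instance of a new toxicity has nothing to match. The requirement that no other factor can reasonably explain the event is also hard to meet here. Every subject has cancer, and some may continue checkpoint inhibitors or targeted therapy (Section 5.1, criterion 4; Section 6.8), so a rival explanation for an immune event is often available.

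The primary objective is safety and tolerability. If sites follow the longer sentence and not the opening one, events drop out of the DLT endpoint and of several rules meant to pause the study or a subject's treatment. Two sites could also classify the same event differently, each with support in the text.

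**Working it through.** The plan gives no attribution rate, error rate or precision target on this point, so there is no figure to reproduce. The check has three parts.

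**1. Applying the text to one event.** Take a first case of an unanticipated event with plausible timing and no evidence for another cause.

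| Provision in Section 10.3.3 | Result |
|---|---|
| *Related*, opening sentence (reasonable possibility) | can be met |
| *Related*, timing | met |
| *Related*, known response | not met |
| *Related*, no other reasonable explanation | may or may not be met |
| *Not related*, evidence supports another cause | not met |

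The opening sentence admits the event, the descriptive sentence rejects it, and *Not related* does not take it either. The definition contradicts itself, and the two categories are not exhaustive.

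**2. Tracing where relatedness is used.**

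| Item | Needs a related call? |
|---|---|
| DLT incidence, primary endpoint (Sections 3, 6.5) | yes |
| AEs and SAEs by relationship, primary endpoint (Section 3) | yes |
| Hold for Grade 4 or higher DLTs in 2 subjects (Section 7.1) | yes, through the DLT definition |
| Hold for at least 3 Grade 3 or higher immunological, CRS or TLS cases (Section 7.1) | yes |
| Individual discontinuation (Section 7.2) | yes |
| Grade 3 or higher immunological event (Section 7.2.1) | no; differs from Section 7.2 |
| SAEs beyond 30 days after last dose (Table 4) | yes |
| Hold for a non-progression death within 30 days (Section 7.1) | no, for the trigger |
| AEs and SAEs overall and by severity (Sections 3, 9.3.3) | no |

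**3. Illustrating the size.** Let p be the true per-subject probability of a SUPLEXA-caused event and s the share of such events classified as *Related*. Both are assumptions. The classified rate is q = p × s.

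Chance of no related event in n = 15 (the DLT group in Section 6.5): (1 − q)^15. With p = 0.20:

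- s = 1: 0.80^15 = 0.035
- s = 0.5: 0.90^15 = 0.206
- s = 0.25: 0.95^15 = 0.463

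Chance of at least 3 cases in n = 60 (planned enrolment, Section 9.1, at most one case per subject): 1 − Σ C(60,k) q^k (1 − q)^(60−k) over k = 0, 1, 2. With p = 0.10:

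- s = 1: 0.947
- s = 0.5: 0.583
- s = 0.25: 0.190

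Taking n = 15 for the more than 15 subjects in Section 2.3.1, zero related events has a two-sided 95% Clopper-Pearson upper limit of 1 − 0.025^(1/15) = 21.8%. That limit applies to the classified rate. If s were 0.5, it would correspond to a true rate of up to 0.218 / 0.5 = 43.6%. The 21.8% itself reflects only the small sample and would be the same under any definition.

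The direction is downward whenever s is below 1. The amount depends on s, which the documents do not give.

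**The case against.** The strongest reply is that the opening sentence of *Related* is the operative test, that the longer sentence merely describes a typical case, and that the Investigator's clinical judgment governs. Known response need not mean seen in patients. Table 1 lists CRS, TLS, infection, neurologic events and flu-like symptoms with fever as possible risks, and the IB, which is not available here, is said to contain the reasonably expected events. On that reading only unanticipated toxicities are exposed. This has weight and limits the scope, but it does not remove the inconsistency or supply a category for the unanticipated event.

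Three stronger conclusions might be inferred, and the documents do not support them.

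- *That all safety oversight is driven towards zero.* The death hold needs no related call to trigger and continues while the relationship is unclear. Overall AE and SAE incidence is a primary endpoint. The Data Safety Monitoring Board (DSMB) sees all relevant toxicity data and may recommend halting. The Sponsor as well as the Investigator can call a DLT related, and Section 6.5 says that worsening of pre-existing illness should not be excluded from consideration as a DLT.
- *That this rule produced the zero count in Sections 2.3.1 and 4.3.* The documents show neither the recorded AEs nor how any was classified. Subjects were enrolled under earlier protocol versions whose causality text is not available. Section 2.3.1 also says that nothing had been observed in laboratory results or reported AEs.
- *That rewording Section 10.3.3 would by itself repair DLT counting.* Section 6.5 has its own exclusion for events reasonably attributable to disease, progression or concomitant medication.

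**Conclusion.** The point holds as an internal inconsistency with a known direction of bias. Section 10.3.3 gives two incompatible standards for *Related* and leaves an unexplained new event unclassifiable. Read literally, it lowers the DLT count, the two relatedness-based holds, the individual discontinuation rules, late SAE collection and related-AE incidence, with the greatest effect on unexpected events. The death-hold trigger and all-cause AE and SAE incidence are not affected.

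The size is unknown. The illustrative probabilities rest on assumed values of p and s and show only that a moderate loss of attribution could matter at these sample sizes. The absence of related events reported so far neither confirms nor refutes under-attribution. Because Section 4.3 relies on that absence, the classification behind it should be sound.

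**What to change.** 1. In Section 10.3.3, Causality Categories, define *Related* by the reasonable-possibility standard already given under Assessment of Causality. List known pattern and alternative causes as considerations, not requirements.
2. Define *Not related* as no reasonable possibility, so that the two categories cover every event.
3. In the primary safety tables, present all-cause Grade 3 or higher AEs beside the related ones, so that the conclusion does not rest on attribution alone.
4. Re-review the AEs already recorded under the corrected wording before the absence of treatment-related events is relied on in Section 4.3.
5. The sponsor should reconcile Sections 6.5 (with its separate disease-attribution exclusion), 7.1, 7.2 and 7.2.1 with the corrected definition. Section 7.2 requires relatedness for Grade 3 or higher immunological events and Section 7.2.1 does not. Which rule should apply is a clinical decision for the sponsor, and none is proposed here.

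The cost is a wording amendment, a memo to sites, one added table and a single re-review of recorded AEs. The downside is that the related-AE count may rise.
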